6.2 Subject Disposition

Disposition will be summarized for Part I, Part II, and the study overall.

For Part I, the number of subjects who were screened, were screen failures, were randomized to treatment, included in the Safety, ITT, and PP, completed Part I (i.e., attended Week 16 visit) and prematurely discontinued from the study during Part I (along with the reasons for discontinuation) will be presented.

For Part II, the summary will present the number and percentage of subjects who were re-randomized for Part II, completed Part II (i.e., attended Week 32 visit) and prematurely discontinued from the study during Part II (along with the reasons for discontinuation).

For the study overall, the summary will present the number of subjects who were screened, were screen failures, were randomized to treatment, included in the Safety, ITT, and PP, attended the visits at Weeks 16 and 32, completed the study (week 36) and prematurely discontinued from the study at any time (along with the reasons for discontinuation).

Subjects who discontinued from the study for reasons related to the COVID-19 pandemic will be identified through manual review. Their number and percentage will be summarized separately.

Number and percentage of subjects who did not attend a visit for reasons related to COVID-19 will be provided by visit and treatment group.

All disposition information will be listed. Also, a listing of enrollment details will provide the date of informed consent and inclusion/exclusion criteria not met, if any.

6.3 Demographic and Baseline Characteristics

Demographic and baseline characteristics will include:

- age
- sex
- race
- ethnicity
- baseline height, weight, and body mass index (BMI)
- Baseline vIGA score
- Baseline EASI score
- Baseline BSA (%)
- Baseline SCORAD score
- Baseline PP-NRS score
- time since atopic dermatitis diagnosis (years)

- whether the subject took any prior biologic therapy for atopic dermatitis

Descriptive statistics will be presented for continuous variables. Frequency counts and percentage will be presented for categorical variables. Height will be presented in centimeters, weight in kilograms and BMI in kg/m².

Age will be derived from Informed Consent Date and Date of Birth as the number of whole years between those two dates.

These analyses will be performed for the ITT populations.

All demographic parameters and baseline characteristics will be presented in the by-subject listings.

6.4 Medical History

Medical history will be summarized by Medical Dictionary of Regulatory Activities (MedDRA), Version 25.0, System Organ Class and Preferred Term. One subject will be counted once for each applicable Preferred Term and System Organ Class. This summary will be performed for the ITT population. All medical history information will be listed.

6.5 Atopic Dermatitis History

Time since diagnosis of atopic dermatitis in years will be calculated as the year of the screening visit minus the year of diagnosis. History of prior use of medications and types of medications for atopic dermatitis (includes biologics, JAK inhibitors, topical corticosteroids) will be derived from the prior medication data by a manual review. History of intolerance to topical corticosteroids will be derived from the medical history data by a manual review.

Time since diagnosis will be summarized descriptively. Number and percentage of subjects with history of prior use of each type of atopic dermatitis medications and with history of intolerance to topical corticosteroids will be presented.

6.6 Ophthalmological History

Number and percentage of subjects with each finding of past ocular history and each type of ocular surgery as collected at the Ophthalmological History eCRF will be presented by treatment group.

All ocular history conditions and surgeries will be listed.

6.7 Protocol Deviations

Protocol deviations will be derived algorithmically as well as reported by sites. A subset of protocol deviation will be classified as affecting proper administration of the treatment or accurate evaluation of its effectiveness and thus excluding from the PP population. Specific deviation, their severities and rules for their algorithmic detection are defined in the separate Protocol Deviations Specification document.

COVID-19 related protocol deviations will be identified through manual review and will be marked in the listing.

All reasons for exclusion from the PP population will be summarized by reason category and treatment group and listed. This analysis will be performed for the ITT population. The final

determination of which protocol deviations exclude subjects from the PP population will be made by the sponsor during the blinded data review prior to the database lock.

Number and percentage of subjects who underwent re-[REDACTED] will be presented separately for Part I and Part II by treatment group for the Safety population. Number of missed doses in the [REDACTED] period will be summarized descriptively and also categorically (0, 1, 2, etc. missed doses) separately for Part I and Part II by treatment group for the Safety population.

6.9 Efficacy Analyses

6.9.1 Analysis of the primary and key secondary endpoints

6.9.1.1 Primary analysis

The primary analysis will be performed on the ITT population.

Subjects in the ITT population with missing EASI at Week 16 or missing baseline will be imputed as non-responders for the primary endpoint. Similarly, subjects in the ITT population with missing vIGA at Week 16 or missing baseline will be imputed as non-responders for the key secondary endpoint.

Additionally, the subjects with intercurrent events, i.e. those who took any rescue medications (systemic or topical) prior to Week 16, took any prohibited medications prior to Week 16 (as determined by blinded data review) and discontinued the study drug prior to Week 16 will be considered non-responders for both the primary and key secondary endpoint. Subjects will be known to take systemic rescue medications prior to Week 16 if this is recorded at the “Rescue Medications” CRF or “Concomitant Medications” CRF or the subject attended any of “Systemic Rescue Medications Visits” 7 to 10. Topical rescue medications will be identified through a review of the “Concomitant Medications” CRF.

For both primary and key secondary endpoint the number and percentage of subjects achieving the endpoint will be provided. Comparisons between each active group and the placebo group will be performed pairwise. Each comparison will be done using Cochran-Mantel-Haenszel (CMH) test stratified [REDACTED]

If all strata have no subject in one of the treatment groups, a value of 0.1 will be added to all cells in the corresponding table in order to prevent dividing by 0, as suggested in Greenland and Robins (1985). The estimates of Mantel-Haenszel common risk (response rate) difference between each active dose group and placebo, along with 95% confidence interval, will be provided. The p-value from the Breslow-Day test for homogeneity of strata will also be provided. If the p-value of the Breslow-Day test is ≥ 0.05 , the treatment-by-strata interaction is not significant. In the case of heterogeneity between the strata, in-depth analysis will be conducted to understand the source of the interaction; Fisher’s exact test will be used instead of CMH.

Tests for superiority over placebo for the primary and the key secondary endpoint will be conducted using a hierarchical closed testing step-down approach to preserve the overall Type I error rate of 0.05. Testing would begin with the highest dose for the primary endpoint, and if statistically significant at alpha (α) 0.05, then move to the highest dose for the key secondary endpoint, followed by the middle dose for the primary endpoint, then the middle dose for the key secondary endpoint, and so on until the lowest dose for the key secondary endpoint is reached.

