2.2 Primary Estimand

The primary estimand is defined as follows:

Population of interest	Subjects with moderate to severe atopic dermatitis
Outcome Measure/Endpoint	Achieving at least 75% improvement in EASI at Week 16
Treatment	SCD-044 [REDACTED] and [REDACTED] mg once daily
Intercurrent Event	Use of rescue medication (systemic or topical), use of prohibited medications (as determined during blinded data review) and early treatment discontinuation. Composite strategy will be applied to these intercurrent events and the subjects with intercurrent events will be treated as non-responders.
Population-level Summary Measure	Difference in proportions between each the active treatment arms and placebo arm

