For each pair of (X1, X2), X1% of subjects will be randomly drawn from the subjects with missing values or intercurrent events in placebo group and X2% of subjects will be randomly drawn from the subjects with missing values or intercurrent events in the active group. These randomly selected X1% subjects in the placebo and X2% subjects in the active group will be imputed as responders. The remaining subjects with missing endpoint value or intercurrent events will be imputed as non-responders. Analysis then will be conducted using the combined observed data and imputed data for each treatment group using the CMH test as described for the primary analysis in section 6.9.1.1. The random draw procedure will be repeated 49 times for each pair of (X1, X2) and the median p-value for the active vs. placebo comparison will be used for the conclusion. The estimate of the CMH common risk (response rate) difference between the treatment groups associated with the p-value selected as median will also be shown. If the same median p-value is obtained in more than one of the 49 random draws, the largest difference will be selected. The random seed for the draw will be preset as 441916 to ensure the analysis is repeatable and amenable to validation via double programming. If one pair of X1 and X2 is found to reverse the study conclusion (i.e., median p-value > 0.05 [tipping point analysis will be performed only if the primary analysis reached p-value ≤ 0.05]), then these parameters will be the tipping points.

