6.9.1.4 Subgroup analyses

The primary analysis of the primary and key secondary endpoints will also be repeated by subgroups:

In case when subgrouping variable was used as the stratification factor for the primary analysis, this variable will not be used as a stratification variable for the analysis of this subgroup.

The Breslow-Day test will be performed for each subgrouping variables in order to verify the homogeneity of endpoints. In the case of sparse data Fisher's exact test will be used instead of CMH.

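### SAP 6.9.1.1 swaps the stratified CMH test for Fisher's exact test when strata look heterogeneous; the trigger is on the odds-ratio scale and the swap costs some power without gaining validity

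*SAP*

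**What the plan says.** SAP 6.9.1.1 specifies a pairwise CMH test of each active dose against placebo (the stratification factors are redacted). With it come the "estimates of Mantel-Haenszel common risk (response rate) difference between each active dose group and placebo", a 95% confidence interval, and a Breslow-Day p-value. At p ≥ 0.05, the SAP states, "the treatment-by-strata interaction is not significant". It then says: "In the case of heterogeneity between the strata, in-depth analysis will be conducted to understand the source of the interaction", and that Fisher's "exact test will be used instead of CMH".

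Four other places bear on this:

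- **SAP 2.2** gives the summary measure as "Difference in proportions between each the active treatment arms and placebo arm". SAP 2.4 does the same for the key secondary endpoint.
- **SAP 6.9.1.1** sets a fixed test sequence: "Testing would begin with the highest dose for the primary endpoint". It alternates between the two endpoints down to the lowest dose, making six tests.
- **SAP 6.9.1.2** runs the tipping-point analysis "using the CMH test as described for the primary analysis in section 6.9.1.1".
- **SAP 6.9.1.4** also calls on Fisher's test, but there the condition is "In the case of sparse data".

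**The concern.** The confirmatory test depends on a pretest made on the same data. Two things are left open: what happens at p < 0.05 is only implied, and the SAP does not say whether Fisher's test is pooled over strata. Taking the natural reading (trigger at p < 0.05, pooled Fisher), there are four problems:

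1. **Scale.** Breslow-Day tests equality of odds ratios, while the estimand is a risk difference. If placebo rates differ by stratum, a constant risk difference implies unequal odds ratios.
2. **Remedy.** Pooled Fisher ignores the strata, so it says nothing about an interaction between them, and it is conservative. Sparse data, the reason given in 6.9.1.4, is a different problem.
3. **Coherence.** The estimate and interval stay stratified while the p-value becomes pooled, so the two can disagree.
4. **Tipping point.** That analysis names only CMH. Its 0%/0% cell uses the same imputed data as the primary analysis, but after a switch it need not return the primary p-value.

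The rule applies to every test in the sequence. If the switch costs the high-dose primary test its significance, the other five tests are closed.

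**Working it through.** **Inputs.** Two-sided α = 0.05 (SAP 6.1); about 240 subjects (protocol 4.1); allocation 3:1:1:3 (SAP 3.1). 240 × 3/8 = 90 and 240 × 1/8 = 30, so the comparisons are 90 v 90 (high dose) and 30 v 90 (other doses). Response rates, CMH factors and stratum sizes are not visible, so those below are assumptions. The public text gives no power figure to reproduce.

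**Scale mismatch.** Take a constant 20-point difference with placebo rates of 5% and 25%:

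- OR₁ = (0.25/0.75)/(0.05/0.95) = 6.33
- OR₂ = (0.45/0.55)/(0.25/0.75) = 2.45

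Nothing varies on the estimand's scale, but Breslow-Day sees two different odds ratios.

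**Worked example, 90 v 90.** Stratum 1: 12/30 v 9/30 (+10.0 points). Stratum 2: 7/60 v 0/60 (+11.7 points). This table was found by searching for one that shows the effect.

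- *CMH* = [Σ(a − E)]²/ΣV, with E = n₁m/n and V = n₁n₀m(n − m)/[n²(n − 1)], where m is the number of responders in the stratum. E = 10.5 and 3.5; V = 3.470 and 1.662. (1.5 + 3.5)²/5.132 = 4.87, p = 0.027.
- *Breslow-Day* = Σ(a − ã)²/Var(ã), with ã the count expected under the Mantel-Haenszel odds ratio of 2.85. ã = 13.97 and 5.11; variances 3.127 and 1.317. 1.25 + 2.73 ≈ 3.97 (unrounded sum) on 1 df, p = 0.046, so the switch fires.
- *Pooled Fisher*, 19/90 v 9/90: p = 0.063.
- *Mantel-Haenszel difference*, weights n₁n₀/n = 15 and 30: (15 × 0.1000 + 30 × 0.1167)/45 = 0.111. With the Sato standard error of 0.0493 the 95% CI is 1.4 to 20.8 points.

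Near-identical stratum differences are labelled heterogeneous, and the test fails while the planned interval excludes zero.

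**Simulation of the rule**, 5,000 trials per scenario, 90 v 90 (all figures in %; losses in points):

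| Scenario | Switch fires | Power, always CMH | Power, SAP rule | Loss | In switched trials: CMH / Fisher |
|---|---|---|---|---|---|
| 2 strata, constant difference 20, placebo 10/20 | 7.3 | 88.7 | 88.5 | 0.2 | 87.3 / 84.8 |
| same, placebo 5/25 | 17.7 | 90.4 | 89.3 | 1.1 | 86.2 / 79.6 |
| same, placebo 3/30 | 27.1 | 89.9 | 87.9 | 2.0 | 86.8 / 79.2 |
| same, placebo 2/40 | 34.7 | 89.7 | 85.3 | 4.4 | 87.1 / 74.7 |
| 8 strata, constant difference 20, placebo 4 to 32 | 5.8 | 86.2 | 85.9 | 0.3 | 83.0 / 77.4 |
| 2 strata, true interaction, differences 35 and 5 | 63.1 | 88.2 | 85.9 | 2.3 | 87.8 / 84.2 |

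At 30 v 90 the switch fires in 7.1% to 26.8% of two-strata trials with a constant difference. At placebo 5/25, power is 66.9% with CMH throughout and 66.0% under the rule.

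**Second set**, 20,000 trials per scenario, 2 or 8 strata of several sizes, constant differences of 15 or 20 points, narrower placebo spreads:

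- *Trigger rate:* 5–6% with a common odds ratio of 3. With a constant risk difference, 6–19% (two strata) and 5–8% (eight strata). With a true interaction, 15–72%.
- *Overall power loss:* 0.1–1.3 points with a common odds ratio or constant risk difference; 0.6–3.8 points with a true interaction.
- *Power loss in switched trials:* 2–10 points (for example 64% to 55% at 30 v 90).
- *Fisher non-significant while the Mantel-Haenszel CI excludes zero:* 2–11% of switched 90 v 90 trials, against 0.1–1.2% for the CMH test when there is no switch. At 30 v 90, at most 1.4%.

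**Type I error.** 4.5–5.0% under the rule across both sets, and 4.5–5.1% with CMH throughout. Exact enumeration puts the unstratified Fisher test's actual size at 3.0–3.7%. The switch therefore buys no error control that CMH lacks.

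**The case against.** The strongest reply is that little is lost. The rule is pre-specified and error control is intact. The larger power losses are conditional on the switch firing. In 4,000-trial runs with two equal strata, placebo 20/10 or 25/5 and a constant 20-point difference, a significant CMH result became non-significant in only 0.4% and 0.7% of all 90 v 90 trials, so loss of the whole sequence this way is rare. That stands.

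Three randomization factors also make eight strata the more natural layout. There a constant risk difference triggers the switch only slightly more often than the nominal 5%. That stands too, although the CMH factors are redacted and a coarser stratification cannot be excluded. The high trigger rates under a true interaction show Breslow-Day doing its job and are not false alarms. The worked example was searched for and needs a 0/60 cell, so it shows what is possible, not what is likely.

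Two points on wording are fair. The in-depth analysis does explore heterogeneity; it is the replacement test that does not. And the tipping-point cross-reference could be read as carrying the whole of 6.9.1.1, fallback included, which makes that point an ambiguity more than a contradiction.

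None of this supplies a reason for the switch. CMH remains a valid test of no association in any stratum when effects differ between strata. With two equal strata at 90 v 90, the switch never turned a non-significant CMH result into a significant one.

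**Conclusion.** The concern holds. The switch rests on a pretest whose scale differs from the estimand's, replaces a valid stratified test with a conservative unstratified one, and leaves a stratified interval beside a pooled p-value. It is a matter of efficiency and coherence, not of validity. Averaged over all trials the loss is usually about one point or less with a constant risk difference. It reaches about 4 points only with a true interaction or very unequal placebo rates. These sizes rest on assumed response rates and strata, a p < 0.05 trigger and a pooled Fisher test. The direction does not depend on the rates chosen. It should be fixed because the change is free and any contradiction would fall on a confirmatory result.

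**What to change.** In SAP 6.9.1.1:

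- Keep the stratified CMH test, and the Mantel-Haenszel risk difference with its confidence interval, as the confirmatory analysis whatever the Breslow-Day result.
- Report Breslow-Day and the stratum-specific risk differences descriptively, and label the in-depth analysis exploratory.
- Delete the switch to Fisher's test.

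The primary test then also matches the CMH test named for the tipping-point analysis. The cost is SAP wording only; design, data collection and sample size are unchanged.

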6.9.1.2 Sensitivity analyses

The following sensitivity analyses will be performed to explore the effects of missing data on the primary endpoint and the key secondary endpoint:

1. Analysis similar to the primary analysis on the ITT population, but with missing endpoints imputed using Last Observation Carried Forward (LOCF) approach. For this

analysis the latest available post-baseline assessment of EASI will be carried forward to impute missing Week 16 assessments. Subjects with missing baseline or no post-baseline assessment prior to Week 16 will be excluded from this analysis. Additionally for subjects with intercurrent events, i.e. those who took topical or systemic rescue medications prior to Week 16, took prohibited medications prior to Week 16 or discontinued treatment prior to Week 16 the last available post-baseline assessment obtained prior to the start of the rescue medication will be used to impute Week 16 assessment. If no post-baseline assessment obtained prior to the intercurrent event (start of rescue medication, start of prohibited medication, discontinuation of treatment) is available, such subject will be excluded from this analysis.

2. Analysis similar to the primary analysis on the ITT population, but with missing endpoints imputed using Active Treatment Worst Case (ATWC) approach. For this analysis any subjects in the Placebo group with missing response or with an intercurrent event will be imputed as responders, while any subjects in any active treatment group with missing response or with an intercurrent event will be imputed as non-responders.
3. Tipping point analysis. This analysis will consist of a series of analyses similar to the primary analysis of the primary and key secondary endpoints with varying proportions of subjects with missing endpoint value or with intercurrent events imputed as responders or non-responders. The analysis will be performed for each active treatment group vs. placebo and for each combination of X1, the percentage of subjects with missing endpoint value or with intercurrent events in the placebo group and X2, the percentage of subjects with missing endpoint value or with intercurrent events in the active group. Both X1 and X2 will range from 0% to 100% in steps of 25%.

For each pair of (X1, X2), X1% of subjects will be randomly drawn from the subjects with missing values or intercurrent events in placebo group and X2% of subjects will be randomly drawn from the subjects with missing values or intercurrent events in the active group. These randomly selected X1% subjects in the placebo and X2% subjects in the active group will be imputed as responders. The remaining subjects with missing endpoint value or intercurrent events will be imputed as non-responders. Analysis then will be conducted using the combined observed data and imputed data for each treatment group using the CMH test as described for the primary analysis in section 6.9.1.1. The random draw procedure will be repeated 49 times for each pair of (X1, X2) and the median p-value for the active vs. placebo comparison will be used for the conclusion. The estimate of the CMH common risk (response rate) difference between the treatment groups associated with the p-value selected as median will also be shown. If the same median p-value is obtained in more than one of the 49 random draws, the largest difference will be selected. The random seed for the draw will be preset as 441916 to ensure the analysis is repeatable and amenable to validation via double programming. If one pair of X1 and X2 is found to reverse the study conclusion (i.e., median p-value > 0.05 [tipping point analysis will be performed only if the primary analysis reached p-value ≤ 0.05]), then these parameters will be the tipping points.

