2.4 Key secondary estimand

The key secondary estimand is defined similar to the primary estimand as follows:

Population of interest	Subjects with moderate to severe atopic dermatitis
Outcome Measure/Endpoint	Achieving a vIGA of '0' or '1' with at least 2-point reduction from baseline at Week 16
Treatment	SCD-044 [REDACTED], [REDACTED] and [REDACTED] mg once daily
Intercurrent Event	Use of rescue medication (systemic or topical), use of prohibited medications (as determined during blinded data review) and early treatment discontinuation. Composite strategy will be applied to these intercurrent events and the subjects with intercurrent events will be treated as non-responders.
Population-level Summary Measure	Difference in proportions between each the active treatment arms and placebo arm

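### The SAP's missing-data sensitivity analyses also re-impute intercurrent-event subjects, whose outcome the composite estimand already fixes as non-response

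*SAP*

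**What the plan says.** **Intercurrent events.** SAP 2.2 lists rescue medication, prohibited medication and early treatment discontinuation, and states that "the subjects with intercurrent events will be treated as non-responders". SAP 2.4 does the same for the key secondary endpoint: "Composite strategy will be applied to these intercurrent events". SAP 6.9.1.1 carries this into the analysis: subjects with such an event before Week 16 "will be considered non-responders for both the primary and key secondary endpoint".

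**Missing values.** SAP 6.9.1.1 has a separate rule: "Subjects in the ITT population with missing EASI at Week 16 or missing baseline will be imputed as non-responders". It has a matching rule for vIGA.

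**Sensitivity analyses.** SAP 6.9.1.2 introduces its three analyses as "performed to explore the effects of missing data on the primary endpoint" and on the key secondary endpoint. It then specifies:

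- LOCF: for event subjects, "the last available post-baseline assessment obtained prior to the start of the rescue medication will be used to impute Week 16 assessment". Event subjects with no usable earlier assessment are left out.
- ATWC: "any subjects in the Placebo group with missing response or with an intercurrent event will be imputed as responders", while active-arm subjects with either condition count as non-responders.
- Tipping point: in each arm, missing and event subjects form one pool. A random X1% (placebo) or X2% (active) of the pool become responders, on a grid from 0% to 100% in steps of 25%.

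**Protocol.** Section 9.8 defines ATWC by missing assessments alone and leaves the tipping-point method to the SAP. SAP section 8 says that event handling has been expanded, without saying how this affects these three analyses.

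**The concern.** Under a composite strategy, an event subject has a known outcome: non-response. Nothing about that outcome is missing, whether or not a Week 16 score was recorded. A missing-data sensitivity analysis should hold the estimand fixed and vary only what is assumed about values that were not observed. The three analyses in 6.9.1.2 vary both at once.

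The cost is in interpretation. If ATWC loses significance, or the grid produces a tipping point, a reader of the study report would take the result to be fragile to missing data. The cause could instead be that rescue users and discontinuers on placebo were reclassified as responders, against the estimand. How far the result moves would then depend on how many subjects had an event, not only on how many had missing data.

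**Working it through.** **1. Status of each subject type under the rules as written**

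| Subject type | Primary analysis | ATWC | Tipping point | LOCF |
|---|---|---|---|---|
| Missing, no event | Non-responder | Placebo responder, active non-responder | X1% / X2% responders | Last value carried, or excluded |
| Event, Week 16 missing | Non-responder | Same as above | Same pool | Pre-event value, or excluded |
| Event, Week 16 observed | Non-responder | Same as above | Same pool | Pre-event value, or excluded |

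Only the first row is purely a missing-data question. The protocol's ATWC covers the first two rows; the SAP's covers all three.

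**2. How the analyses are linked.** The tipping-point cell X1=0%, X2=0% is the primary analysis. The cell X1=100%, X2=0% is the SAP's ATWC. The mixing in ATWC therefore also runs through the grid.

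**3. Size for ATWC.** The documents give about 240 subjects (protocol 4.1) in a 3:1:1:3 ratio (SAP 3.1). Placebo and high dose each have 240 × 3/8 = 90. One placebo flip changes the difference by 1/90 = 1.1 points.

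The visible text gives no response, missing-data or event rates, so the responder counts below are assumptions. So is the figure of 4 placebo subjects missing without an event. The test is unstratified, because the CMH strata are redacted:

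z = (pA − pP) / √[p̄(1 − p̄)(1/90 + 1/90)], with p̄ the pooled proportion.

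Example, 30/90 v (10 + 9)/90: difference 11/90 = 0.1222; p̄ = 49/180 = 0.2722; standard error √(0.2722 × 0.7278 × 2/90) = 0.0664; z = 1.84; p = 0.066.

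| High dose v placebo | Primary | 4 missing-only flips | Total flips at which p first exceeds 0.05 | Event flips beyond the 4 |
|---|---|---|---|---|
| 30/90 v 10/90 | 22.2 points, p=0.0003 | 17.8, p=0.006 | 9 (12.2 points, p=0.066) | 5 |
| 36/90 v 14/90 | 24.4 points, p=0.0003 | 20.0, p=0.003 | 10 (13.3 points, p=0.058) | 6 |
| 45/90 v 14/90 | 34.4 points, p<0.001 | 30.0, p<0.001 | 18 (14.4 points, p=0.0502) | 14 |

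The last column depends on the assumed 4. With u placebo subjects missing without an event, it is 9 − u, 10 − u and 18 − u.

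**4. Tipping point, first scenario.** With only the 4 missing subjects in the placebo pool, X1=100% and X2=0% gives p=0.006, so no cell tips. With 5 event subjects added, the pool is 9. X1=75% (6 or 7 flips) gives p=0.017 or 0.027, and X1=100% gives p=0.066. The reported tipping point exists only because event subjects are in the pool.

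**5. LOCF.** A pre-event score can make an event subject in either arm a responder, and event subjects without one leave the ITT comparison. The cut-off wording also conflicts. One sentence ties the carried value to the start of rescue alone, although it concerns all three event types. The next looks for an assessment "prior to the intercurrent event (start of rescue medication, start of prohibited medication, discontinuation of treatment". For a subject who only discontinued or took a prohibited medication, the first sentence gives no cut-off. For one who discontinued and later took rescue, the two sentences can select different values.

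**The case against.** The strongest reply is that these are prespecified stress tests, openly described, and that section 8 declares expanded event handling. For ATWC the departure can only make the comparison harsher: active event subjects stay non-responders, so ATWC as written never looks better for the drug than a missing-only run. A pass is then stronger evidence. This stands, but it does not help with a fail, whose cause would be unclear.

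A second reply is that the contrast with a missing-only ATWC overstates the departure from the protocol, whose rule flips every missing Week 16 value whatever the cause. That is right. Against the protocol rule, the SAP adds only event subjects with an observed Week 16 value. The documents do not say how many there will be, or whether scores are collected after rescue or after stopping drug. If all 5 event subjects in the first scenario lacked a Week 16 value, the protocol rule would also give 12.2 points.

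A reader might infer that pooling tilts the analyses in the drug's favour, because LOCF and cells with X2 above 0% can turn active event subjects into responders. The documents do not support that. Both rules also act on placebo, cells with X2 above 0% help the active arm in any two-way grid, and the tipping point runs only after a significant primary result. What can be said is that the direction is not fixed.

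**Conclusion.** The concern holds as a mismatch between stated purpose and method. SAP 6.9.1.2 changes the event strategy and the missing-data assumption together, so its results cannot be read as robustness to missing data. For ATWC the effect is one of added harshness, about 1.1 points per placebo event subject flipped. Whether that matters depends on the observed effect: in the illustrations, 5 to 14 placebo event subjects remove significance when 4 others are missing. These counts rest on assumed rates and an unstratified test; the planned stratified CMH test would give somewhat different p-values.

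It would be wrong to infer that the main result is at risk. The primary analysis applies the composite rule consistently, and the testing order and type I error are untouched. The point is worth correcting because the sensitivity results will be quoted as evidence about missing data.

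**What to change.** 1. Add missing-only versions of ATWC, the tipping point and LOCF that keep every event subject as a non-responder. Use these for any statement about robustness to missing data.
2. Also run ATWC by the protocol 9.8 rule: all missing Week 16 assessments, whatever the cause.
3. Keep the pooled versions, but move them to SAP 6.9.1.3 and label them as supplementary analyses under a different intercurrent-event strategy.
4. Report by arm the numbers missing without an event, with an event and Week 16 missing, and with an event and Week 16 observed. If the first group is very small, say so, because the missing-only runs will then hardly differ from the primary analysis.
5. In LOCF, set the cut-off at the first intercurrent event of any type, in both sentences.

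The cost is SAP wording, a few extra runs and one count table, with no new data. The change is best made before the Part I unblinding described in SAP section 7.
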